#### **5.4.2 HANDLING OF PARTICIPANT WITHDRAWALS OR TERMINATION**

Participants will be informed in the consent process that they may discontinue the study at any time.

### **5.5 PREMATURE TERMINATION OR SUSPENSION OF STUDY (STUDY STOPPING RULES)**

As stated above, the anticipated risks of participating in this study are low. Should study PI ([name]) believe at any point in the study that participation is detrimental to the participant's health, they will end the subject's participation and refer the subject to other relevant treatment resources as appropriate (i.e., mental health resources).

If, after three consecutive months of active recruitment and enrollment, investigators are unable to sufficiently recruit patients to conduct a single intervention group, consideration of an alternative design (i.e., multiple baseline single arm) will be considered. Following modification of design due to low enrollment, if after three consecutive months of active recruitment and enrollment investigators are unable to sufficiently recruit patients to conduct a single intervention group, the trial will be considered not feasible for implementation and terminated.

## **6 STUDY THERAPY**

### **6.1 STUDY THERAPY AND CONTROL DESCRIPTION**

#### **Intervention Groups**

*Treatment as usual.* Treatment as usual will include ongoing provision of usual treatment options for pain management. This includes continued medication management for cancer related chronic pain by prescribing providers (e.g., oncologist, primary care provider), and access to supportive oncology services (e.g., social work). It may also include other behavioral pain management such as physical therapy, acupuncture, or massage. Psychotherapy (e.g., Cognitive Behavioral Therapy) is often used as TAU in chronic pain. All participants may pursue this treatment modality, as it is part of standard care; however, for participants randomized to the intervention condition, their specified psychotherapy will be the ACT group protocol. Data regarding participation in these services will be collected as stated above in section 5.3.

*ACT Intervention.* Intervention group participants will attend eight weekly, 90-minute, in person, group-based ACT sessions. Groups may occur in person or remotely (i.e., audio/visual teleconferencing). Groups will be initiated with no more than 10 participants and no fewer than 4 participants. If a new group is scheduled with 4-10 participants and enough patients are “no-shows” that cause the group number to fall below 4, the group will continue as is and this will not be considered a deviation. Sessions will be adapted from an efficacious ACT chronic pain treatment manual [14, 15]. Sessions will include key theoretical ACT constructs and strategies as they relate to chronic pain. A licensed clinical psychologist or licensed clinical social worker trained in ACT will facilitate all sessions. Participants in the ACT intervention group will also continue to receive medication management and other behavioral management interventions as described above in “treatment as usual”. Data regarding participation in these services will be collected as stated below in section 7.1.

See Table 2 for more detail.

Table 2. ACT Intervention Constructs/Targets

ACT Session	Topic/Targeted Component	Aims/Application to Chronic Pain
Session 1 – Introductions and Basic Foundations of Treatment	

• Group Introductions

• Introduction to Chronic Pain and Cancer

• Creative Hopelessness

	

• Group introductions and ground rules

• Familiarizing group members with the treatment aims

• Evaluate the usefulness of previous control strategies for pain

• Foster psychological flexibility and awareness around the difficulty of controlling pain

Session 2 – Options and Setting a Course for Treatment	

• Behavior Change

• Mindfulness

	

• Introduction, discussion and application of the tripartite behavioral model in order to understand how thoughts and emotions impact behaviors

• Introduction to mindfulness practice

Session 3 – “Learning to Live” with Chronic Pain	

• Acceptance

• Values

• Mindfulness

	

• Foster acceptance around unhelpful internal events that may get in the way of coping around chronic pain

• Identifying and clarifying personal values

• Continued development of mindfulness practice

Session 4 – Values and Action	

• Values

• Goal Setting

• Committed Action

• Mindfulness

	

• Continued clarification of personal values

• Differentiating values and goals

• Understanding barriers that might occur when engaging in valued actions

• Continued mindfulness practice

Session 5 – Urges, Thoughts, & Feelings	

• Cognitive Defusion

• Mindfulness

	

• Introduction to concept of cognitive defusion

• Practice creating space between unhelpful thoughts that may increase suffering or interfere with valued behaviors

• Continued mindfulness practice

PI: [name]

Protocol #: 18-1102

Version Date: 03/30/2021

Session 6 – Action-Getting Your Feet Moving	

• Treatment Review

• Committed Action

• Mindfulness

	

• Review of treatment progress and any areas of ongoing concern

• Planning for action

• Fostering willingness around potential internal barriers

• Continued mindfulness practice

Session 7 – Commitment	

• Willingness

• Committed Action

• Mindfulness

	

• Extended discussion of willingness

• Fostering commitment to actions and values even in the face of barriers

• Continued mindfulness practice

Session 8 – Lifelong Maintenance	

• Maintenance

	

• Fostering commitment

• Relapse prevention and setbacks

• Saying goodbye to group

---

#### **6.1.1 DURATION OF THERAPY**

For the ACT intervention group, an 8-week therapy protocol will be used.

---

#### **6.1.2 TRACKING OF THERAPY**

Attendance to weekly group sessions will be tracked in order to monitor the number of therapy sessions received.

## 7 STUDY PROCEDURES AND SCHEDULE

### 7.1 STUDY PROCEDURES/EVALUATIONS

After a participant has been consented, he or she will be randomized to either the ACT intervention group or the TAU condition as described in section 6.1. All participants will complete baseline, mid-point, post-intervention, and follow-up assessments. Further information for each assessment time point is provided below in this document under section 7.2. Also, see Table 3 for assessment schedule.

Table 3. Assessment schedule for all study participants

Assessments/ Measures	Baseline Assessment	Intervention Mid-Point (Wk 4) and Post-Intervention (Wk 8)	6 Wk Follow-up	12 Wk Follow-Up
Physical/Emotional Functioning (SF-36)	X	X	X	X
Pain Interference/Intensity (PROMIS)	X	X	X	X
Psychological Flexibility measures (CPAQ and CAAQ)	X	X	X	X

Study measures will include the following:

*Adherence.* Adherence to the intervention will be measured by completion of all relevant assessments and, for intervention group members, attendance to therapy sessions as outlined above and completion relevant assessments.

*Fidelity.* Fidelity of intervention delivery will be evaluated through structured observational methods. Third-party observers (i.e., not provider or participant) will complete a checklist instrument including all components of the active intervention.

*Demographic information.* Relevant demographic information (e.g., sex, ethnicity, race, education level, marital status, etc.) will be collected from the patient at the pre-intervention assessments (screening and/or baseline), and when necessary, confirmed via EHR. In the case that the electronic chart and patient report differ, patient report will be given priority.

*Medical information.* Relevant medical information will be collected both from the patient at the pre-intervention assessments as well as from chart review of the University of Colorado Hospital electronic health record (EHR). When patient report and EHR are in conflict, EHR data will be preferred. Relevant medical information includes medications pertaining to pain management (e.g., opioid and non-opioid analgesics), medical pain management services (e.g., nerve blocks, spinal cord stimulator), behavioral pain management services (e.g., massage, acupuncture, physical therapy), and medications pertaining to psychiatric symptoms (given their impact on the primary outcome). Other relevant medical information will include data directly related to the patient's cancer treatment, including diagnosis, as well as type and duration of treatment.

*Physical/Emotional Functioning.* The Medical Outcomes Study 36-item short-form health survey (SF-36) is a self-report measure of health related quality of life that includes subscales for both physical functioning and emotional well-being [17]. The physical functioning subscale includes 10 items evaluating the occurrence and severity of physical difficulties, with a higher subscale score indicating better levels of physical functioning. The subscale specifically asks, “Does your health now limit you in these activities? If so, how much?”, and then provides a number of activities related to daily living (e.g., climbing stairs, bathing or dressing) as well as exercise behaviors (e.g., walking more than one mile, vigorous activities such as strenuous sports). Item responses are made on a 3-point Likert scale with one indicating “Yes, limited a lot,” two indicating “Yes, limited a little,” and three indicating “No, not limited at all.” This subscale has excellent internal consistency with a Cronbach’s alpha of .93 [18].

The emotional well-being subscale of the SF-36 includes five items evaluating how patients have felt during a previously identified period, with a higher subscale score indicating higher levels of positive affect. Specifically, items ask questions such as “Have you been a very nervous person?” and “Have you felt calm and peaceful?” Item responses are made on a six point Likert scale with one indicating “All of the time” and six indicating “none of the time.” This subscale has excellent internal consistency with a Cronbach’s alpha of .90 [18].

*Pain Intensity and Interference.* The National Institute of Health’s Patient-Reported Outcomes Measurement Information System (PROMIS) pain intensity instrument evaluates how much a person hurts [20]. This study will use the PROMIS Scale v1.0- Pain Intensity 3a short form, which assesses pain intensity over seven days using two items, including pain intensity at its worst and average pain intensity. It also evaluates current pain levels. All items are rated on a 1-5 rating scale with 1 as “had no pain” and 5 as “very severe”. The pain interference instrument [21] evaluates the impact of pain on various domains of living, including participation in social, cognitive, emotional, physical, and recreational activities. This study will use the PROMIS scale v1.0- Pain Interference 8a, which includes eight total items asking the patient to recall the extent of pain interference over the past seven days. All items are rated on a 1-5 rating scale with 1 as “not at all” and 5 as “very much”. For all items in the PROMIS pain item bank the score metric is Item Response Theory (IRT). Both measures provide an IRT-based T-score and Standard Error [20, 21].

*Psychological Flexibility Measures.* The Chronic Pain Acceptance Questionnaire (CPAQ [19]) is a 20-item self-report measure of experiential acceptance in pain populations. This measure has two unique and psychometrically reliable subscales, including activity engagement ( $\alpha = .82$ ) and pain willingness ( $\alpha = .78$ ) [19]. Examples of items from the activities engagement subscale include “There are activities I do when I feel pain” and “I lead a full life even though I have chronic pain.” Examples of items from the pain willingness subscale include “I need to concentrate on getting rid of my pain” and “I avoid putting myself in situations where my pain might increase.” A 0-6 Likert rating scale indicates how true each statement is for the patient with 0 as “never true” and 6 as “always true.”

The Cancer Acceptance and Action Questionnaire (CAAQ [20]) is an 18-item self-report measure of disease specific experiential avoidance. Items on this measure have been adapted from other disease specific versions of the Acceptance and Action Questionnaire [21] to the cancer experience. For example, items include statements such as “I try to avoid reminders of my cancer” and then participants are asked to rate how true this statement is on a 1-7 Likert scale

with one as “never true” and 7 as “always true.” This measure has shown excellent internal consistency when used in a heterogeneous cancer sample ( $\alpha = .91\text{-.95}$ ) [20].

## 7.2 STUDY SCHEDULE

### 7.2.1 SCREENING

#### Participant Screening and Assessment

*Participant screening.* In addition to screening conducted via recruitment methods described above, all participants will be screened either in person, via telephone, or video conference with a standardized screening form. Verbal consent will be obtained by research staff prior to administering the standardized screening form, which will be included on the screening form. The screening form will assess 1) inclusion criteria, 2) exclusion criteria and 3) a pain interference measure. The pain interference measure will include a single item pulled from the Chronic Pain Grading Questionnaire [23]. Participants eligible for the study will rate their level of interference with their daily activities from their cancer-related pain as 4 or higher on a scale of 0 = no interference to 10 = unable to carry on any activities. This scale has been used as a screening tool in similar psychotherapy trials for non-cancer related chronic pain [18]. After verbally consenting, eligible participants will be randomized to either the ACT plus TAU intervention condition or the TAU alone condition. Participants found to be ineligible will be provided with a packet for alternative resources for interdisciplinary pain management (e.g., CU pain psychology services and CU integrative medicine services) either in person or via email.

### 7.2.2 ENROLLMENT/BASELINE

*Baseline Assessment.* Eligible participants will be scheduled for an initial baseline appointment with research staff held either in person or done remotely (i.e., video conference or over the phone). During this baseline appointment, participants will complete the informed consent process and all questions will be answered by research staff. After providing consent, participants will be randomized. Patients will then be asked to complete their baseline measures, if it is feasible; however, participants may also have the option of completing these measures via a REDCap HIPAA secure link from their own personal computer. Baseline assessment measures will be completed within a two-week period prior to the initiation of the intervention. For patients who are randomized to the TAU arm, the next time point after baseline will be the Week 4 assessments, which should be completed at 4 weeks (+/- 7 days) of the baseline assessments. For patients who are randomized to the ACT arm, the next time point after baseline will be the scheduled Week 1 ACT intervention group session. Specific baseline measures (SF-36, PROMIS, CPAQ, and CAAQ) may be repeated in order to be within the specified two-week window.

---

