## 4 STUDY DESIGN AND ENDPOINTS

### 4.1 DESCRIPTION OF THE STUDY DESIGN

This study is a single site (University of Colorado Cancer Center), randomized control trial. It will investigate the implementation (i.e., feasibility, acceptability, and fidelity) and preliminary clinical efficacy of an ACT intervention plus TAU for chronic pain in cancer survivors compared to TAU alone. Following consent, participants will provide baseline data including demographic and clinical characteristics. Participants will be randomized to ACT plus TAU or TAU alone. Due to study design, it is not possible to blind either participants or investigators to study condition. Participants will complete assessments at baseline, 4-week intervention midpoint, 8-week intervention completion, 6-week follow-up, and 12-week follow-up.

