### 7.2.7 SCHEDULE OF EVENTS TABLE

	Screening	Baseline	8-week intervention period 								Follow-up Assessments 		Qualitative Interview
			Wk 1	Wk 2	Wk 3	Wk 4	Wk 5	Wk 6	Wk 7	Wk 8	Post 6-Wk 	Post 12-Wk 	
Consent		X											
Pre-Screen	X												
Eligibility		X											
Demographics	X	X											
Randomization 		X											
ACT session 1 			X										
ACT session 2 				X									
ACT session 3 					X								
ACT session 4 						X							
ACT session 5 							X						
ACT session 6 								X					
ACT session 7 									X				
ACT session 8 										X			
Likert Scale – Acceptability 			X	X	X	X	X	X	X	X			
SF-36		X 				X 					X 	X 	X 
PROMIS		X 				X 					X 	X 	X 
CPAQ		X 				X 					X 	X 	X 
CAAQ		X 				X 					X 	X 	X 
Qualitative Interview 													X

1. Determined by pre-screen chart review, screening phone call (with verbal consent), and confirmation of eligibility by research study personnel, after patient consents.
2. After consent and before completion of baseline measures.
3. ACT (intervention) participants only.
4. Within 2 weeks prior to intervention start date. These measures may be repeated in order to be within window.
5. +/- 7 day window
6. The qualitative interview may be conducted via phone or in person, any time from Week 9 through 12-Week follow-up; for ACT participants only.

7. Intervention and Follow up visits can be completed in person or remotely.

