## 10.5 MEASURES TO MINIMIZE BIAS

### 10.5.1 ENROLLMENT/ RANDOMIZATION/ MASKING PROCEDURES

There is no blinding in this study. Enrolled participants will be randomly assigned at a 1:1 ratio to receive eight weekly group-based ACT sessions plus TAU or TAU alone. The REDCap randomization tool will be used to facilitate randomization.

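### Randomisation precedes the self-reported baseline in an unblinded trial, and nothing withholds the allocation until the questionnaires are submitted

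*Combined protocol and SAP*

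**What the plan says.** Section 7.2.2 sets the order at the baseline appointment: "After providing consent, participants will be randomized. Patients will then be asked to complete their baseline measures, if it is feasible". Footnote 2 of the schedule of events (7.2.7) times randomisation as "After consent and before completion of baseline measures".

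The questionnaires need not be completed at that appointment, since "participants may also have the option of completing these measures via a REDCap HIPAA secure link from their own personal computer". They may also be done again. Footnote 4 of the schedule reads "Within 2 weeks prior to intervention start date. These measures may be repeated in order to be within window", and 5.3 and 7.2.2 allow the same repeat.

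On blinding, 4.1 says "it is not possible to blind either participants or investigators to study condition" and 10.5.1 says "There is no blinding in this study". Section 10.5.1 names the REDCap tool for randomisation but does not say when the result is given to the participant.

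The overview in 4.1 reads the other way. It has participants give baseline data, including demographic and clinical characteristics, after consent, and mentions randomisation in the next sentence.

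Sections 7.1 ("After a participant has been consented, he or she will be randomized to either the ACT intervention group or the TAU condition") and 7.2.1 ("After verbally consenting, eligible participants will be randomized to either the ACT plus TAU intervention condition or the TAU alone condition") place randomisation after consent but do not place it relative to the questionnaires.

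In the analysis, 10.3.3 and 10.3.10 compare the arms by repeated measures ANOVA over five time points, the first of which is baseline (4.1). Section 10.3.5 compares the baseline scores with t-tests.

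**The concern.** A baseline score should be fixed before the arm can influence it. Here the four questionnaires are patient-rated, the patient is not blinded, and the operative text collects the answers after the arm has been drawn. Completion from home, or a repeat before a late group start, lengthens the time in which the arm may be known. The repeat is tied to the intervention start, which TAU participants do not have, and the text does not say how the rule works for them.

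The treatment effect on the SF-36 and the exploratory scales is a group-by-time contrast that includes baseline. A reaction that is present at baseline and gone by follow-up would look like a difference in change. Hope in the ACT arm or disappointment in the TAU arm would work against ACT; the opposite reaction would favour it. The t-tests in 10.3.5 cannot separate such a reaction from chance imbalance.

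At stake are the secondary and exploratory comparisons. Feasibility, acceptability and fidelity do not use these scores.

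**Working it through.** **The order of steps.** Section 7.2.2 and footnote 2 are explicit: consent, randomisation, questionnaires. Section 4.1 suggests the reverse, but does not require the four questionnaires to be complete and does not hold back the allocation. Sections 7.1 and 7.2.1 fit either order. No section says when participants learn their arm.

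The plan gives no figure for a reaction to allocation, so there is nothing to reproduce. What follows is an illustration.

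**Inputs from the plan.**
- 92 participants for clinical outcomes (10.4), allocated 1:1 (10.5.1): 46 per arm.
- Pre-post correlation r = .5 and effect d = 0.61 (10.4).
- One-tailed alpha .05 (10.3.1).
- Five time points (10.3.3).

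**Assumptions, not in the plan.**
- Baseline shift between arms s = 0.1, 0.2 or 0.3 SD.
- Share of the shift persisting at later time points p = 0, 0.5 or 1.
- For the F-test: compound symmetry with r = .5, and d = 0.61 at all four later time points.

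**Bias.** The baseline contrast carries s and each later contrast carries p·s. The change contrast is therefore off by (1 − p)·s in absolute size. With p = 1 it is zero.

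**Five-time-point group-by-time F-test.** Let D be the net difference in change. One time point sits at 0 and four at D, so the sum of squares about the mean is (4D/5)² + 4(D/5)² = 0.8D². The noncentrality is (46/2) × 0.8D² / (1 − 0.5) = 36.8D², with 4 and 360 degrees of freedom.
- No shift, d = 0.61: 36.8 × 0.61² = 13.7; power 85.3%.
- No treatment effect, s = 0.2, p = 0: 36.8 × 0.04 = 1.47; rejection 13.4%.

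| Persistence | Rejection under no effect, s = 0.1/0.2/0.3 | Power if the shift works against ACT |
|---|---|---|
| p = 0 | 6.9 / 13.4 / 26.4% | 68.8 / 47.8 / 28.1% |
| p = 0.5 | 5.5 / 6.9 / 9.4% | 77.9 / 68.8 / 58.5% |
| p = 1 | 5.0% throughout | 85.3% throughout |

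**One-tailed t-test on a single change score.** The SD of change is √(2(1 − 0.5)) = 1, so the noncentrality is D × √(46/2) on 90 degrees of freedom. With no shift and d = 0.61, power is 89.6%.

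| Persistence | False positives if the shift favours ACT, s = 0.1/0.2/0.3 | Power if it works against ACT |
|---|---|---|
| p = 0 | 12.1 / 24.4 / 41.4% | 78.3 / 62.0 / 43.3% |
| p = 0.5 | 8.0 / 12.1 / 17.6% | 84.6 / 78.3 / 70.7% |
| p = 1 | 5.0% throughout | 89.6% throughout |

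**What moving the baseline changes.** If the questionnaires precede randomisation, the baseline carries no reaction, but later scores still carry p·s, and the contrast then includes p·s. At p = 0.5 this equals the bias under the present order, 0.5s. At p = 1 the present order cancels the reaction, whereas with the baseline first it stays in the comparison (F-test rejection 6.9/13.4/26.4% with no other effect).

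**The case against.** Several points on the other side stand.

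- **Being randomised is not being told.** The documents do not give the time of disclosure, so the bias needs a step that the text leaves open. A reader might infer that baselines are in fact contaminated, or that ACT results will be inflated. Neither is supported: the text shows only that nothing prevents a reaction from entering, and its direction cannot be derived.
- **Section 4.1 gives the other order.** It does, but 7.2.2 and footnote 2 are the more specific text. The conflict is a reason to clarify.
- **The largest percentages depend on complete fading and a change-score proxy.** The planned ANOVA gives smaller figures, and the shift is assumed throughout. One shift for every scale is also crude. The PROMIS interference items and two of the three intensity items look back seven days (7.1). Completed at the appointment, they mostly describe days before allocation.
- **Moving the baseline does not remove a lasting reaction.** True, as the last step of the working shows. A reaction that persists belongs to the comparison of two open-label strategies; a reaction in the baseline is contamination of the reference score.
- **The repeat keeps baseline close to the group start.** That is a legitimate aim. Footnote 4, unlike footnote 3, is not limited to ACT participants, so a reader should not infer that the repeat is reserved for one arm. The text simply does not say how it works in TAU.

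**Conclusion.** The point holds as a gap in protection. The operative text randomises before the four patient-rated baseline questionnaires, the trial is unblinded, no section withholds the arm until they are submitted, and 4.1 suggests a different order. The order of steps is certain; that a bias follows is possible but not shown.

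Under the assumed shifts, the planned F-test at 46 per arm would reject under no effect in anything from the nominal 5% (reaction fully persistent) to 26% (0.3 SD, fully faded). The results rest on r = .5 and compound symmetry as well as on the assumed shift and fade.

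The primary implementation outcomes are untouched and the efficacy aim is labelled preliminary. The change is nevertheless worth making because it is cheap and protects the reference score of every secondary and exploratory comparison.

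**What to change.** 1. In 7.2.2 and footnote 2, require the four questionnaires to be submitted, at the appointment or by link, before the REDCap randomisation is run. Failing that, require submission before the allocation is disclosed to the participant. Align 4.1, 7.1 and 7.2.1.
2. State that a reaction persisting to follow-up remains part of the open-label comparison under either order, so the change protects the baseline but does not remove all effects of unblinding.
3. Where a late group start leads to a repeat, apply the same repeat rule in both arms, keep both scores, and report the analysis once with the pre-randomisation score and once with the repeat.
4. Keep participants already enrolled in the main analysis. Flag those whose baseline followed randomisation, and add a sensitivity comparison of follow-up scores that does not use that baseline. At r = .5 it loses no power against a change score, since both have SD 1 (89.6% one-tailed at 46 per arm), but it retains any persisting reaction.

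**Cost.** No sample size changes. Some randomisations will wait for a form, some consented people may leave before randomisation, and some baselines will be older when a group starts. Section 5.3 dates the in-person phase from 1/1/2019 and this version is dated 03/30/2021, about 27 months into a 3-year study if the clock began then. The data will therefore contain two baseline regimes, possibly with most participants under the present order.
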